7.6.1 Deaths

See Core Safety SAP.

7.6.2 Serious Adverse Events

See Core Safety SAP.

7.6.3 Adverse Events Leading to Discontinuation of Study Therapy

See Core Safety SAP.

7.6.4 Adverse Events Leading to Dose Delay

AEs leading to dose delay will be summarized for all treated subjects by treatment arm:

- Overall summary of AEs leading to dose delay by worst CTC grade (grade 1, 2, 3, 4, 5, unknown) presented by SOC/PT

The analysis will be conducted using the 30-day safety window and repeated using the 100-day safety window.

By-subject listing of AEs leading to dose delay will be provided.

7.6.5 Adverse Events

See Core Safety SAP.

In addition, a shift table of worst on-treatment CTCAE grade compared with baseline CTCAE grade per subject will be presented by PT. The analyses will be conducted using the 30-day safety window and repeated using the 100-day safety window.

7.6.6 Immune Mediated Adverse Events (IMAEs)

IMAEs are specific events defined as:

- Events occurring within 100 days of the last dose;
- Regardless of causality;
- With no clear alternate etiology based on investigator assessment, with data collected on a new CRF page;
- Treated with immune-modulating medication. (Of note, adrenal insufficiency, hypothyroidism/thyroiditis, hyperthyroidism, diabetes mellitus, and hypophysitis are considered IMAEs regardless of immune-modulating medication use, since endocrine events are often managed without immune-modulating medication).

The IMAE data collection process is presented in [Figure 7.6.6-1](#) and [Table 11.3](#) provides the list of preferred terms that will be subject to evaluation as IMAEs.

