## 1.5 Overall Risk/Benefit Assessment

Treatment options with chemotherapy and targeted therapy offer limited benefits in overall survival. Patients with squamous histology have a worse prognosis and do not benefit from new treatments. Newer agents have also provided limited improvement in OS for non-squamous patients. These patients face an unmet medical need. Nivolumab demonstrated survival benefit over standard of care docetaxel across histology in 2 randomized Phase 3 trials. In addition, the safety profile for the nivolumab-treated patients was favorable compared to docetaxel. The platinum-based chemotherapy regimens have similar clinical activity and well described safety profiles, characterized by myelosuppression and other regimen-specific non-hematologic toxicities, such as peripheral neuropathy, nausea/vomiting, and renal impairment. The safety profile of nivolumab is characterized by immune-related toxicities, such as diarrhea, rash, pneumonitis, liver toxicity, and endocrinopathies, which are manageable with established algorithms.

The optimal dosing frequency of administration that balances a favorable safety and efficacy profile with convenience and adherence for the patient is not yet known. This trial requires patients to receive nivolumab therapy at 3 mg/kg or 240 mg Q2W for up to 12 months (52 weeks) and demonstrated clinical benefit (CR, PR, or SD) on 2 consecutive tumor assessments prior to the study enrollment.

In Study 209003, 296 patients were randomized to receive nivolumab at 1 mg/kg, 3 mg/kg, or 10 mg/kg. A maximum tolerated dose was not defined at the doses tested. Drug-related Grades 3 or 4 toxic effects occurred in 14% of patients who received nivolumab, suggesting no new safety signals. Established algorithms provide for successful management of immune-related AEs via drug delay or glucocorticoids. It was noted in CA209003 that approximately 80% of patients achieved a durable clinical benefit by 4 months after treatment. With a minimum follow-up of over 1 year, 45% of patients maintained their clinical response.

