##### **4.5.1 Dose Delay Criteria**

Nivolumab administration should be delayed for the following:

- Grade 2 non-skin drug related AEs, with the exception of fatigue
- Grade 2 drug-related creatinine, AST, ALT and/or Total Bilirubin abnormalities
- Any Grade 3 skin, drug-related AE
- Any Grade 3 drug-related laboratory abnormality, with the following exceptions:
  - Grade 3 lymphopenia or asymptomatic amylase or lipase does not require dose delay
  - Grade  $\geq$  3 AST, ALT, Total Bilirubin will require dose discontinuation

- Any AE, laboratory abnormality, or intercurrent illness which, in the judgment of the investigator, warrants delaying the dose of study medication.

Subjects who require delay of nivolumab should be re-evaluated weekly or more frequently if clinically indicated and resume nivolumab dosing when re-treatment criteria are met.

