## 6 ADVERSE EVENTS

An *Adverse Event (AE)* is defined as any new untoward medical occurrence or worsening of a preexisting medical condition in a clinical investigation subject administered study drug and that does not necessarily have a causal relationship with this treatment. An AE can therefore be any unfavorable and unintended sign (such as an abnormal laboratory finding), symptom, or disease temporally associated with the use of study drug, whether or not considered related to the study drug.

The causal relationship to study drug is determined by a physician and should be used to assess all adverse events (AE). The causal relationship can be one of the following:

Related: There is a reasonable causal relationship between study drug administration and the AE.

Not related: There is not a reasonable causal relationship between study drug administration and the AE.

The term "reasonable causal relationship" means there is evidence to suggest a causal relationship.

Adverse events can be spontaneously reported or elicited during open-ended questioning, examination, or evaluation of a subject. (In order to prevent reporting bias, subjects should not be questioned regarding the specific occurrence of one or more AEs.)

BMS will be reporting adverse events to regulatory authorities and ethics committees according to local applicable laws including European Directive 2001/20/EC and FDA Code of Federal Regulations 21 CFR Parts 312 and 320.

Suspected Unexpected Serious Adverse Reaction is a serious adverse event that is both unexpected and related to an IMP or comparator IMP, for which expedited reporting to clinical investigators, Ethics Committees and Health Authorities is required (Previously known as ESR).

Immune-mediated adverse events are AEs consistent with an immune-mediated mechanism or immune-mediated component for which non-inflammatory etiologies (eg, infection or tumor progression) have been ruled out. IMAEs can include events with an alternate etiology which were exacerbated by the induction of autoimmunity. Information supporting the assessment will be collected on the participant's case report form.

Every adverse event must be assessed by the investigator with regard to whether it is considered immune-mediated. For events which are potentially immune-mediated, additional information will be collected on the participant's case report form.

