7.6.6.1 Incidence of IMAE

See Core Safety SAP.

IMAEs will be summarized by treatment arm:

- Overall summary of IMAEs by worst CTC grade (grade 1, 2, 3, 4, 5, unknown) presented by Category/PT
- Overall summary of IMAEs by worst CTC grade (grade 1, 2, 3, 4, 5, unknown), where immune modulating medication was initiated, presented by Category/PT
- Overall summary of IMAEs by worst CTC grade (any grade, grade 3-4, grade 5), where immune modulating medication was initiated, presented by Category/PT
- Overall summary of any Endocrine IMAEs by worst CTC grade (grade 1, 2, 3, 4, 5, unknown) presented by Category/PT
- Overall summary of any Endocrine IMAEs by worst CTC grade (any grade, grade 3-4, grade 5) presented by Category/PT
- Overall summary of serious IMAEs by worst CTC grade (any grade, grade 3-4, grade 5), where immune modulating medication was initiated, presented by Category/PT
- Overall summary of Endocrine serious IMAEs by worst CTC grade (any grade, grade 3-4, grade 5) presented by Category/PT
- Overall summary of IMAEs leading to discontinuation by worst CTC grade (grade 1, 2, 3, 4, 5, unknown), where immune modulating medication was initiated, presented by Category/PT
- Overall summary of IMAEs leading to discontinuation by worst CTC grade (any grade, grade 3-4, grade 5), where immune modulating medication was initiated, presented by Category/PT
- Overall summary of Endocrine IMAEs leading to discontinuation by worst CTC grade (grade 1, 2, 3, 4, 5, unknown) presented by Category/PT
- Overall summary of Endocrine IMAEs leading to discontinuation by worst CTC grade (any grade, grade 3-4, grade 5) presented by Category/PT
- Overall summary of IMAEs leading to dose delay by worst CTC grade (grade 1, 2, 3, 4, 5, unknown), where immune modulating medication was initiated, presented by Category/PT
- Overall summary of IMAEs leading to dose delay by worst CTC grade (any grade, grade 3-4, grade 5), where immune modulating medication was initiated, presented by Category/PT
- Overall summary of Endocrine IMAEs leading to dose delay by worst CTC grade (grade 1, 2, 3, 4, 5, unknown) presented by Category/PT
- Overall summary of Endocrine IMAEs leading to dose delay by worst CTC grade (any grade, grade 3-4, grade 5) presented by Category/PT

The analyses will be conducted using the 100-day safety window.

By-subject IMAE listing will be provided.

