7.6.9 Immune modulating medication

The percentage of subjects who receive immune modulating concomitant medication for

- management of adverse event
- other use

will be reported separately for each treatment arm (percentages of treated subjects by medication class and generic term).

Management of select AEs

For each category/subcategory of select AEs (see [Table 11-2](#)), the following will be reported for each treatment arm:

- Percentage of subjects who received immune modulating concomitant medication for management of any select AE in the category among subjects who experienced at least one select adverse event in the category/subcategory.
- The total duration of immune modulating concomitant medication for select adverse event management.

These analyses will be performed on any select AEs, drug-related select AEs, select endocrine AEs and drug-related select endocrine AEs.

The analysis will be conducted using the 30-day safety window.

Management of IMAEs

For each category of IMAEs, the following will be reported for each treatment arm:

- Percentage of subjects who receive immune modulating concomitant medication for management of IMAE in the category among subjects who experience at least one IMAE in the category.
- The total duration of immune modulating concomitant medication for IMAE management.

The analysis will be conducted using the 100-day safety window.

Management of other events of special interest

For each category of other events of special interest, the following will be reported for each treatment arm:

- Percentage of subjects who receive immune modulating concomitant medication for management of other events of special interest in the category among subjects who experience at least one other event of special interest in the category.
- The total duration of immune modulating concomitant medication for other events of special interest management.

The analyses will be conducted using the 100-day safety window.

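### SAP 7.6.6 counts a non-endocrine IMAE only if it was treated with immune-modulating medication, so the 7.6.9 treated percentage is fixed at 100% there and no planned table shown gives protocol-defined IMAEs by arm

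*SAP*

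**What the plan says.** **SAP 7.6.6** lists the criteria for an IMAE: onset within 100 days of the last dose, any causality, no clear alternate etiology in the investigator's assessment, and "Treated with immune-modulating medication. (Of note, adrenal insufficiency, hypothyroidism/thyroiditis, hyperthyroidism, diabetes mellitus, and hypophysitis are considered IMAEs regardless of immune-modulating medication use".

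**SAP 7.6.9**, under management of IMAEs, plans by arm, for each category, this statistic: "Percentage of subjects who receive immune modulating concomitant medication for management of IMAE in the category among subjects who experience at least one IMAE". Both counts refer to the same category, and the duration of such medication is reported as well.

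**SAP 7.6.6.1** plans an overall IMAE summary by worst grade, then a series of summaries limited to events "where immune modulating medication was initiated, presented by Category/PT". The IMAE summaries for discontinuation and for dose delay carry the same limit, except for the endocrine versions.

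**Protocol Section 6** defines the term differently: "Immune-mediated adverse events are AEs consistent with an immune-mediated mechanism or immune-mediated component for which non-inflammatory etiologies" have been excluded. It adds that "IMAEs can include events with an alternate etiology which were exacerbated by the induction of autoimmunity". Medication is not mentioned. The investigator must assess every AE for whether it is immune-mediated, and extra CRF data are collected where it may be.

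**The concern.** A percentage whose numerator must equal its denominator cannot describe how events were managed. The same definition makes a non-endocrine IMAE count depend partly on whether immune-modulating treatment was given, and not only on whether the event occurred.

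The protocol itself expects some immune-related events to be handled without such drugs. Section 1.5 states: "Established algorithms provide for successful management of immune-related AEs via drug delay or glucocorticoids". Section 4.5.1 delays dosing for "Grade 2 non-skin drug related AEs, with the exception of fatigue". Section 4.5.2, on resuming after Grade 2 hepatic abnormalities, makes corticosteroid management conditional on need. An event of this kind can be immune-mediated under the protocol and yet not be an IMAE under the SAP.

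Safety and tolerability by arm is a secondary objective, and the two documents use one term for two different sets of events without saying so.

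**Working it through.** The plan states no figure on this point, so there is none to reproduce. The check is set logic, followed by a short illustration.

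**Step 1. The 7.6.9 percentage.** For category c, let I be the subjects with at least one SAP-defined IMAE in c, and T the members of I given immune-modulating medication for an IMAE in c. The planned statistic is 100 × |T| / |I|.

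- Category with no exempt condition: every event that puts a subject in I was treated, by 7.6.6. So T = I, and the result is 100 × |I| / |I| = 100% in both arms for any data.
- Endocrine category: exempt events enter I with or without medication, so T can be any subset of I and the result can lie anywhere from 0% to 100%.

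**Step 2. The paired IMAE summaries.** By the same logic, the overall IMAE summary and the summary limited to events with medication initiated (7.6.6.1) contain the same non-endocrine events. The two populations described for time to resolution (7.6.6.3) also coincide there. This takes 'treated with' and 'initiated' to mean the same thing at event level.

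**Step 3. The two definitions side by side.**

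| Feature | Protocol Section 6 | SAP 7.6.6 |
|---|---|---|
| Basis | Mechanism, other causes excluded | Listed criteria, investigator assessment |
| Medication needed | No | Yes, except five endocrine conditions |
| Alternate etiology | Allowed if exacerbated by autoimmunity | No clear alternate etiology |

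**Step 4. Where a non-endocrine immune-mediated event without medication is shown.**

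| Output | Shown? |
|---|---|
| All IMAE tables, including IMAEs leading to dose delay | No |
| AEs leading to dose delay (7.6.4), 30- and 100-day windows, with listing | Yes, if it delayed a dose; by SOC/PT, with no immune-mediated label |
| Select AEs (7.6.7) | Yes, if its term is listed and it falls in the 30-day window |
| Other events of special interest (7.6.8), 100-day window | Only in six named categories |
| General AE outputs | Yes, without an immune-mediated label |

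An event arising 31 to 100 days after the last dose cannot delay a dose and falls outside the select AE window. Unless it belongs to one of the six special-interest categories, it appears only in general AE outputs.

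**Step 5. Size.** If a share q of otherwise qualifying non-endocrine subjects is managed without medication, the SAP count is (1 − q) × n × incidence. The documents give n: about 350 randomized 1:1, so 350 / 2 = 175 per arm. They give neither the incidence nor q, so both are assumptions here.

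| Assumed incidence | q = 0% | q = 25% | q = 50% | q = 75% |
|---|---|---|---|---|
| 5% | 8.8 | 6.6 | 4.4 | 2.2 |
| 10% | 17.5 | 13.1 | 8.8 | 4.4 |
| 15% | 26.2 | 19.7 | 13.1 | 6.6 |

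Entries are subjects per arm under the SAP definition. In every cell the planned percentage reads 100%. With a denominator that ignores medication it would read 100%, 75%, 50% and 25% across the columns.

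**The case against.** The strongest reply is that little is lost. SAP 7.6.4 states that "AEs leading to dose delay will be summarized for all treated subjects by treatment arm", with no medication criterion. Select AEs are tabulated by category regardless of treatment. SAP 7.6.9 already plans the percentage given immune-modulating medication among all subjects with a select AE in the category, a denominator that does not depend on treatment. Endocrine percentages and the duration of IMAE medication can both vary. Protocol 8.4.3 names select AEs and not IMAEs among its safety analyses, and the IMAE tables are descriptive with no decision attached. Protocol 1.5 also says most high-grade events were manageable with corticosteroids or hormone replacement, so any undercount is probably mainly low grade.

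Most of this stands, and it limits the point. It does not restore a by-arm view of protocol-defined IMAEs: 7.6.4 has no immune-mediated classification, and the select AE incidence and management analyses use 30 days where the IMAE analyses use 100.

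A reader might infer that events managed by delay alone vanish from the report. They do not; they leave only the IMAE tables. A reader might also infer that the arm comparison is biased because steroid use depends on the dosing interval. Nothing in the documents says so: the delay criteria are common to both arms, and the Appendix 2 guidance applies to all regimens.

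The alternate-etiology difference is weaker than the medication one. The protocol also requires other causes to be excluded, and whether an exacerbated event fails the SAP criterion depends on how the investigator records it.

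**Conclusion.** The point holds for non-endocrine categories. There the 7.6.9 IMAE percentage is exactly 100% in both arms and carries no information, and the overall and medication-initiated IMAE summaries coincide. This follows from the SAP text alone. Immune-mediated events managed without medication are absent from the IMAE tables although Protocol Section 6 would include them, and no planned table shown supplies them by arm in the 100-day window.

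How many events are affected, and whether the share differs by arm, cannot be known from the documents. The counts above are illustrations only. Figure 7.6.6-1, Table 11-3 and the Core Safety SAP were not available to check and may hold further IMAE rules or category names. The matter is one of descriptive safety reporting and does not touch the primary analysis. It is still worth correcting, because a planned statistic cannot vary and two documents define the same term differently.

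**What to change.** 1. Keep the program definition in SAP 7.6.6, and state that it is narrower than the definition in Protocol Section 6.
2. Add to SAP 7.6.6.1 one summary by arm of events that the investigator assessed as immune-mediated, within 100 days of the last dose, regardless of medication. Show the medication-treated events as a subset.
3. Use subjects with those events as the denominator of the management-of-IMAEs percentage in SAP 7.6.9. At minimum, drop that percentage for non-endocrine categories.

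The cost is SAP wording and one or two tables. Protocol Section 6 already requires the assessment, so little or no new data collection is needed. There are two downsides. The added table will not be comparable with the sponsor's program-wide IMAE tables. The protocol's change history also shows that IMAE collection and assessment were added in Revised Protocol 04 (09-Feb-2018), while the original protocol dates from 03-Nov-2015. Earlier events may lack the assessment, and the table should carry a footnote saying so.

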7.6.6.1 Incidence of IMAE

See Core Safety SAP.

IMAEs will be summarized by treatment arm:

- Overall summary of IMAEs by worst CTC grade (grade 1, 2, 3, 4, 5, unknown) presented by Category/PT
- Overall summary of IMAEs by worst CTC grade (grade 1, 2, 3, 4, 5, unknown), where immune modulating medication was initiated, presented by Category/PT
- Overall summary of IMAEs by worst CTC grade (any grade, grade 3-4, grade 5), where immune modulating medication was initiated, presented by Category/PT
- Overall summary of any Endocrine IMAEs by worst CTC grade (grade 1, 2, 3, 4, 5, unknown) presented by Category/PT
- Overall summary of any Endocrine IMAEs by worst CTC grade (any grade, grade 3-4, grade 5) presented by Category/PT
- Overall summary of serious IMAEs by worst CTC grade (any grade, grade 3-4, grade 5), where immune modulating medication was initiated, presented by Category/PT
- Overall summary of Endocrine serious IMAEs by worst CTC grade (any grade, grade 3-4, grade 5) presented by Category/PT
- Overall summary of IMAEs leading to discontinuation by worst CTC grade (grade 1, 2, 3, 4, 5, unknown), where immune modulating medication was initiated, presented by Category/PT
- Overall summary of IMAEs leading to discontinuation by worst CTC grade (any grade, grade 3-4, grade 5), where immune modulating medication was initiated, presented by Category/PT
- Overall summary of Endocrine IMAEs leading to discontinuation by worst CTC grade (grade 1, 2, 3, 4, 5, unknown) presented by Category/PT
- Overall summary of Endocrine IMAEs leading to discontinuation by worst CTC grade (any grade, grade 3-4, grade 5) presented by Category/PT
- Overall summary of IMAEs leading to dose delay by worst CTC grade (grade 1, 2, 3, 4, 5, unknown), where immune modulating medication was initiated, presented by Category/PT
- Overall summary of IMAEs leading to dose delay by worst CTC grade (any grade, grade 3-4, grade 5), where immune modulating medication was initiated, presented by Category/PT
- Overall summary of Endocrine IMAEs leading to dose delay by worst CTC grade (grade 1, 2, 3, 4, 5, unknown) presented by Category/PT
- Overall summary of Endocrine IMAEs leading to dose delay by worst CTC grade (any grade, grade 3-4, grade 5) presented by Category/PT

The analyses will be conducted using the 100-day safety window.

By-subject IMAE listing will be provided.

7.6.6.2 Time-to onset of IMAE

See Core Safety SAP.

Time-to onset of the following IMAE will be summarized for each category by treatment arm:

- Time-to onset of any grade IMAE where immune modulating medication was initiated
- Time-to onset of grade 3 to 5 IMAE where immune modulating medication was initiated
- Time-to onset of any grade Endocrine IMAE
- Time-to onset of grade 3 to 5 Endocrine IMAE

The median time-to onset and range summary statistics will be reported.

Additional details regarding the time-to onset definition and censoring rules are described in time-to onset definition subsection of [APPENDIX 1](#).

The analyses will be conducted using the 100-day safety window.

7.6.6.3 Time-to resolution of IMAE

See Core Safety SAP.

Time to resolution of the following IMAE will be summarized for each category by treatment arm:

- Time-to resolution of any grade IMAE where immune modulating medication was initiated
- Time-to resolution of grade 3 to 5 IMAE where immune modulating medication was initiated
- Time-to resolution of any grade Endocrine IMAE
- Time-to resolution of grade 3 to 5 Endocrine IMAE

Time-to resolution analyses are restricted to treated subjects who experienced at least one IMAE from the Category. Time-to resolution where immune modulating medication was initiated analyses are restricted to treated subjects who experienced the specific events where immune modulating medication was initiated from the Category.

The following summary statistics will be reported: percentage of subjects with resolution of the longest duration of IMAEs, median time-to resolution (derived from Kaplan-Meier estimation) and ranges.

See time-to resolution definition subsection of APPENDIX 1 for additional details.

The analyses will be conducted using the 100-day safety window.

